5.5 RANDOMIZATION AND BLINDING

After returning the baseline survey, we will randomize respondents in a 1:1 fashion to intervention or control, stratified by site. To randomize a patient, the Project Director will log onto the study's database system (which will be adapted from the one used in [name] previous studies), enter the subject's unique study ID, confirm eligibility, and confirm that the survey has been received. The database system verifies that all randomization criteria have been satisfied, then assigns a study ID and a group to the subject. The database system will automatically input the date of randomization and the participant's assignment into their study record. The study's Project Director and counselors will have access to treatment assignments. The study's research assistants and our biochemical validation company (Salimetrics, described in section 4.0) will be kept blind to treatment assignments. Intervention participants will be aware of the arm to which they are assigned when they receive the first phone call from a study counselor.

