5.6 STUDY GROUPS

INTERVENTION

Telephone Counseling

Within one week of receiving a completed baseline survey, a counselor will phone intervention participants. Up to 6 contact attempts will be made at different times (i.e., morning, afternoon, evening) during the week. The purpose of the outreach call is to: 1) deliver motivational enhancement to quit smoking, 2) promote self-efficacy, and 3) encourage participants to participate in smoking cessation treatment. The full telephone counseling protocol is characterized by:

- *Motivational enhancement* – We will include motivational enhancement in each of the first several telephone calls and as-needed during later calls to increase patient motivation to quit and reduce relapse.

- ❑ *Multiple sessions* – Participating smokers will receive 8 calls over two months and then, for those who quit in this timeframe, monthly maintenance calls for six months. The initial call will be 30-45 minutes and subsequent calls will be 10-20 minutes.
- ❑ *Relapse-sensitive scheduling* – Participants will receive 4 calls to plan a quit date, three calls in the first two weeks after their Quit Date, when the relapse risk is highest, followed by another call in another two weeks. Patients who are quit at the 8 week call will receive monthly maintenance calls to work through any slips or barriers to continued abstinence.^{11,12}
- ❑ *Problem-solving therapy* – This approach, based on helping the smoker identify and solve expected and actual challenge, is endorsed by the national smoking cessation guidelines.¹³
- ❑ *Stress Reduction* – Our previous work providing tobacco cessation counseling to VA mental health patients identified stress and anxiety as a major barrier toward quitting and long-term abstinence among this population. Our counseling protocol includes stress reduction techniques, such as relaxation and mindfulness exercises,^{11,12} and the incorporation of smoking schedules to remove the link between smoking and stress responses.¹⁴ We will also send stress reduction self-help materials to intervention participants that the counselors will discuss during the counseling.

Medication Requests

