5.7 DATA COLLECTION

All participants will be surveyed by mail at baseline, by mail 2 weeks after enrollment, and by telephone (or mail for non-respondents) at 6 and 12 months from enrollment. Research assistants will make up to 10 attempts at different days and times to reach participants by phone for the 6 and 12 month surveys. If we cannot reach a participant after 10 attempts, we will mail a paper version of the survey with a cover letter (Appendix K) to participants. Patients will receive a \$10 payment as reimbursement for completing each survey.

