5.7.1 Baseline Survey

Smoking questions

- Smoking habits and history.* We will use measures adapted from the California Tobacco Survey¹⁵ that we have used in several previous studies to assess the number of cigarettes smoked per day, number of days smoking per week, and nicotine dependence..¹⁶
- Motivation.* We will assess readiness for change using the Stage of Change scale.¹⁷
- Tobacco treatment used in prior 12 months.* We will ask participants to indicate whether a VA provider talked to them about smoking in the prior 12 months and which tobacco treatments they used in the prior 12 months.
- Health.* We will ask a single item asking participants to rate their general level of health on a 5-point Likert type scale.

5.7.2 2-Week Survey

Sociodemographics

- Demographics.* Age, sex, marital/partnership status, race/ethnicity, education, and occupation will be assessed, as well as text messaging interest and capabilities.
- Environment.* Using questions from the California Tobacco Survey¹⁵ we will assess household tobacco use and restrictions on smoking at home.

Smoking questions

- Smoking habits and history.* We will use measures adapted from the California Tobacco Survey¹⁵ that we have used in several previous studies.
- Self-Efficacy.* Self-efficacy for smoking cessation will be measured with the 14-item Confidence Questionnaire Form¹⁸ which assesses smoking cessation self-efficacy across 14 different situations or mood states.
- Pros and Cons.* We will use the 6-item decisional balance scale which measures positive and negative attitudes toward quitting.¹⁹
- Perceptions regarding tobacco use.* We will also assess perceived control over withdrawal symptoms⁷⁴ and perceived antismoking norms,²⁰⁻²⁴ measures that predict tobacco use.

Health questions

- ❑ *Health habits.* We will use the AUDIT-C^{24,25} to assess alcohol use and a single item measure developed to assess drug use in primary care.²⁶ We will measure frequency, type and quantity of exercise using questions from the National Health Interview Survey.
- ❑ *Comorbidities.* We will assess baseline comorbid conditions using the survey version of the Charlson index.²⁷

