H2: We hypothesize that mental distress and active substance abuse are the strongest baseline predictors of treatment uptake and long-term abstinence in a mental health population.

Method: We will use a generalized linear mixed model approach³⁶ to determine smoking outcomes at 6 and 12 months. Following the recommended best practices in longitudinal data analysis,³⁷ we will use a two-level hierarchical linear model to fit the data. The outcome variable of interest will be the dichotomous cotinine-validated smoking abstinence data. Therefore, a logit model is appropriate at Level 1, where individual outcomes will be fitted for each subject using time as the primary covariate. The parameter estimates from these individual functions will then be entered as dependent variables in Level 2 in which treatment group (PRO vs. UC) is the covariate. This longitudinal analytic approach will help understand to what extent treatment effects differ between 6 and 12 months and whether they show a delayed effect (either increasing or decreasing over time). This will allow us to determine a treatment main effect as well as a treatment by time interaction. Baseline covariates will be included at the patient level (age, sex, race/ethnicity, nicotine dependence, motivation, self-efficacy, mental distress, and current substance use). Inclusion of covariates typically reduces residual errors and thus boosts statistical power as well as allows us to determine factors that affect abstinence to better target intervention design and content.

Power calculations

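### The Aim 2 treatment effect is adjusted for self-efficacy, distress and substance use as baseline covariates, although these are first measured 2 weeks after enrollment, when intervention calls are due to have begun

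*Combined protocol and SAP*

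**What the plan says.** **Model.** Section 6.0 (Aim 2, Method) describes a two-level logit model for validated abstinence at 6 and 12 months. It is to yield a treatment main effect and a treatment-by-time interaction. On covariates it says: "Baseline covariates will be included at the patient level (age, sex, race/ethnicity, nicotine dependence, motivation, self-efficacy, mental distress, and current substance use". They are justified partly by a gain in power. H2 in the same section calls mental distress and active substance abuse the strongest baseline predictors of treatment uptake and long-term abstinence.

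**Timing.** Section 5.5: "After returning the baseline survey, we will randomize respondents in a 1:1 fashion to intervention or control, stratified by site". Section 5.6: "Within one week of receiving a completed baseline survey, a counselor will phone intervention participants". The listed purposes of that call include "2) promote self-efficacy, and 3) encourage participants to participate in smoking cessation treatment". Section 5.7: "All participants will be surveyed by mail at baseline, by mail 2 weeks after enrollment".

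**Instruments.** The baseline survey (5.7.1) covers smoking habits, nicotine dependence, prior tobacco treatment, one general health item and motivation: "We will assess readiness for change using the Stage of Change scale". The 2-week survey (5.7.2) introduces self-efficacy: "Self-efficacy for smoking cessation will be measured with the 14-item Confidence Questionnaire Form". It also introduces the AUDIT-C, used "to assess alcohol use and a single item measure developed to assess drug use in primary care", and the Kessler-6 and Hospital Anxiety and Depression Scale for distress.

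**The concern.** A covariate measured after randomization can carry part of the treatment's effect. Conditioning on it then estimates something other than the total effect of being assigned to proactive outreach. The risk is concrete for self-efficacy: the first call is meant to raise it, and that call is due before it is first measured. Adjustment would then tend to credit part of the benefit to the covariate and pull the reported treatment effect toward the null.

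The predictor question has a related problem. In the intervention arm, an association between a 2-week score and abstinence may partly reflect early response to treatment. H2 also concerns treatment uptake, which may already have started by week 2, so calling the score a baseline predictor claims more than the design provides.

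At stake are the Aim 2 treatment main effect, including the 6-month effect, and the interpretation of H2.

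**Working it through.** **1. When each listed covariate is first measured (sections 5.7.1 and 5.7.2)**

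| Covariate | First survey | Can treatment change it by then? |
|---|---|---|
| Nicotine dependence, motivation | Baseline, before randomization | No |
| Age, sex, race/ethnicity | 2-week | No |
| Self-efficacy | 2-week | Yes; a named target of the first call |
| Mental distress | 2-week | Possible; no early effect documented |
| Current substance use | 2-week | Possible; no early effect documented |

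The planned order is survey return and randomization, first call by about day 7, then the 2-week form at about day 14. Three of the eight covariates are therefore both post-randomization and changeable.

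**2. The plan's own figures (section 6.0, Power calculations)**

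Intervention quit rate: 0.20 × 16% + 0.80 × 4% = 6.4%. For 4% versus 6.4% with 1,920 per arm and two-sided alpha 0.05, power is 0.918 (0.906 with continuity correction), in line with the stated 90%. This is the Aim 1 comparison. It accounts for site only, so nothing below alters it.

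Expected quitters are 0.04 × 1,920 = 76.8 and 0.064 × 1,920 = 122.88.

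- ln OR = ln[(0.064/0.936)/(0.04/0.96)] = 0.495 (OR 1.641)
- SE = √(1/76.8 + 1/1,843.2 + 1/122.88 + 1/1,797.12) = 0.149

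**3. Illustration for self-efficacy**

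This is a large-sample logistic fit of 12-month abstinence on arm and one covariate X. It is simpler than the plan's two-level model. X is N(0,1) in usual care and in intervention non-engagers, and N(d,1) in the 20% who engage. Quit rates are held at 4%, 4% and 16%. The shift d and the odds ratio per SD are assumptions; the documents give neither.

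| OR per SD | d | ln OR at d = 0 | ln OR at d | Removed | In SE |
|---|---|---|---|---|---|
| 1.3 | 0.2 | 0.4969 | 0.4854 | 2.3% | 0.08 |
| 1.3 | 0.5 | 0.4969 | 0.4616 | 7.1% | 0.24 |
| 1.5 | 0.2 | 0.4993 | 0.4823 | 3.4% | 0.11 |
| 1.5 | 0.5 | 0.4993 | 0.4490 | 10.1% | 0.34 |

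On the odds ratio scale, the smallest change is 1.644 to 1.625 and the largest is 1.648 to 1.567. With d = 0 there is no distortion.

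**4. Direction for the set**

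Take distress with an assumed OR of 0.67 per SD. A 0.5 SD rise among engagers moves the log OR from 0.499 to 0.524 (+5%); a 0.5 SD fall moves it to 0.449 (−10%). For two independent covariates (ORs 1.5 and 0.67), self-efficacy +0.5 SD with distress +0.5 SD gives 0.503 to 0.484 (−4%). Self-efficacy +0.2 SD with distress +0.5 SD gives 0.503 to 0.514 (+2%). The sign depends on unknown inputs.

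**5. Treatment-by-time term**

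Assume 6-month quit rates of 5% (usual care), 5% (non-engagers) and 22% (engagers), OR 1.5 and d = 0.5, with one fixed covariate value per patient. The 6-month effect moves from 0.561 to 0.511, while the interaction moves only from −0.0615 to −0.0626.

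**The case against.** **The affected quantity is secondary.** Aim 2 is chiefly about associations, and the longitudinal treatment term is there mainly to compare 6 with 12 months. That contrast barely moves, and Aim 1 supplies a 12-month effect free of these covariates. This stands and limits the consequence. The plan still says the Aim 2 model will determine a treatment main effect, and it does not say that a 6-month effect will be reported without these covariates.

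**The 2-week form may be a split baseline.** Section 5.7.2 calls the comorbidity items on that form baseline, so the label may be deliberate shorthand. That explains the wording, but it does not place the measurement before randomization or before the first call.

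**Exposure by week 2 may be slight.** Reaching a participant can take up to six attempts, and only about 20% are expected to accept treatment. This is fair: the distortion may be small or absent.

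**Pre-enrollment diagnoses exist.** Section 5.7.5 takes a diagnostic category from the 12 months before enrollment. The Aim 2 list, however, names distress and current use, which match the 2-week instruments.

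A reader might also infer two further faults that the documents do not support:

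- **That the propensity-based imputation would mishandle missing 2-week covariates.** Section 6.0 describes it for the outcome and confines its methods to the 6- and 12-month surveys and cotinine validation. It is not proposed for these items.
- **That symptom severity in the Aim 1 reach regression has the same timing problem.** That text names neither an instrument nor a time.

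**Conclusion.** The point holds. Three changeable covariates labelled baseline are measured after randomization, so the adjusted Aim 2 main effect, including the 6-month effect, is not guaranteed to be the total treatment effect. H2's distress and substance-use predictors are 2-week measures. This rests on the schedule alone and needs no assumed number.

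The size is unknown from the documents. It is zero if treatment has not moved the measures by week 2, and about 2% to 10% of the log odds ratio for self-efficacy under the assumptions shown. That is modest and well below one standard error.

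Three stronger readings go too far:

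- **That the trial's efficacy result is biased.** The primary comparison does not use these covariates.
- **That all three adjustments shrink the effect.** A mechanism is documented for self-efficacy only, where the likely bias is toward the null. For distress and substance use no early effect or direction is stated, so the net direction is unknown.
- **That the loss is much larger.** A shift of 0.3 SD across the whole arm would give bigger losses. If only engagers shift, it needs 0.3/0.20 = 1.5 SD among them, and nothing in the documents supports that.

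This should be fixed, but it does not threaten the primary analysis.

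**What to change.** 1. **Treatment-effect model.** Where Aim 2 reports a treatment effect, adjust only for site, variables from the pre-randomization baseline survey (smoking, nicotine dependence, stage of change, self-rated health) and pre-enrollment medical record data such as the section 5.7.5 diagnostic category. Treatment cannot change age, sex or race/ethnicity, but it could affect who returns the 2-week form. Take them from pre-enrollment records where available. Otherwise include them in a way that does not drop non-returners, so that all randomized participants stay in the model.
2. **Predictor model.** Put self-efficacy, Kessler-6 and Hospital Anxiety and Depression Scale scores, AUDIT-C and drug use in a separate model labelled as 2-week measures. State that intervention-arm associations may include early treatment response.
3. **H2.** Relabel distress and substance use as 2-week measures.

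The cost is an analysis-plan edit and one extra model, with no change to the surveys. The treatment-effect model loses some prognostic adjustment, and H2 becomes a statement about patients as they are 2 weeks after enrollment.

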5.3 IDENTIFYING POTENTIAL PARTICIPANTS

Using a three-step process, we will work with VA programmers at our Minneapolis site to identify potential participants using specific combinations of administrative data contained in the EMR system.

Selecting current smokers: Current smokers will be identified using the EMR tobacco use clinical reminder codes, where information is stored as a health factor. Patients will be included if they have screened positive for current tobacco use in the previous six months. We selected six months to reduce the false-positive rate of this sampling method (i.e., reduce the number of patients we contact who are no longer smoking). Patients will be excluded if they have an ICD 9 diagnosis of dementia (i.e., 290.XX or 331.XX).

Identifying Mental Health patients: Within the list of all eligible smokers, VA programmers will identify patients treated in the previous 12 months in a VA Mental Health Clinic, using VA clinic stop codes: 502-581.

Selecting the initial sample: After receiving a list for each site of current smokers with a recent Mental Health visit, we will select *all* women and a random sample of men to total 5,000 potential participants from each site (N=20,000) as our initial recruitment pool. We are selecting all women as an initial recruitment pool to increase the representation of women in our final sample.

Verifying the sample: We will verify our list of eligible patients each month, since we will be sending out letters and surveys to patients each month throughout the enrollment phase. If we relied solely on data collected at the beginning, smoking status could be over a year old on some subjects by the time they received their letter. Each patient who is no longer listed as a current smoker will be replaced by another patient from the site prior to mailing out any materials (and thus prior to enrollment and randomization).

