Method: The study design is a randomized block design with the blocks comprising combinations of the four hospital sites.

We will address the question of Reach via two indices:

- Proportion of patients who respond to the outreach letters and enroll in the study (i.e., completed the baseline survey). This analysis will help us understand the proportion of smokers in Mental Health who will respond to proactive outreach. Given the innovative nature of the proactive outreach approach, we will examine the acceptability of the intervention to determine which patients are more likely to accept treatment in the PRO and UC conditions. Specifically, we will use multivariable logistic regression to determine which baseline characteristics (e.g., age, race/ethnicity, income, mental health diagnosis, symptom severity) are associated with receipt of cessation counseling (state quitline or VA) or use of cessation medications.
- Proportion of patients who engage in at least one treatment session compared to control patients. Specifically, we will determine how many patients in the intervention arm used treatment (counseling and/or medications) and compare this to the number of patients

enrolled in the control arm who report using existing VA tobacco cessation services on the follow-up surveys, which will provide data regarding acceptability of treatment.

The primary smoking outcome variable that is expected to be affected by treatment is dichotomous cotinine-validated abstinence at 12 months post-enrollment. The comparisons of the abstinence rates across the two groups will be made using exact logistic regression methods, accounting for stratification by site, to model the log odds of use of smoking cessation treatment and log odds of 12-month abstinence. Exact logistic regression employs the non-parametric Chi-square test or Fisher's exact test.³⁵ These tests are widely applicable in complete randomized experimental designs that yield contingency tables. Fisher's exact test is particularly suitable for contingency tables with small and unbalanced frequency counts, which are to be expected for the population-based outcome we have chosen where our population quit rate in the control condition is expected to be 4%.

Aim 2: Model longitudinal associations between baseline sociodemographic, medical and mental health characteristics and validated abstinence at 6 and 12 months in the PRO and UC conditions.

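### The Aim 2 predictor model has no term for site, the factor used to stratify randomization and the primary regression, so its predictor associations are open to between-site confounding

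*Combined protocol and SAP*

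**What the plan says.** **Aim 2 model (Section 6.0, Specific aim analysis, Aim 2 Method).** The plan states: "we will use a two-level hierarchical linear model to fit the data". Level 1 is a logit model over time within each participant. The Level 1 estimates are then "entered as dependent variables in Level 2 in which treatment group (PRO vs. UC) is the covariate". Patient characteristics follow: "Baseline covariates will be included at the patient level (age, sex, race/ethnicity, nicotine dependence, motivation, self-efficacy, mental distress, and current substance use". The list is not introduced as a set of examples. Site does not appear as a fixed effect, a random effect, a stratum or a third level.

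**Elsewhere site is part of the structure.**
- Section 5.5: "we will randomize respondents in a 1:1 fashion to intervention or control, stratified by site".
- Section 6.0, Aim 1 Method: "The study design is a randomized block design with the blocks comprising combinations of the four hospital sites". Abstinence is compared between arms "using exact logistic regression methods, accounting for stratification by site".
- Section 6.0, Missing Data: imputation is run separately for each combination of study group and design stratum. That text does not use the word site, but site is the only stratum the documents define.

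**Treatment-receipt regression (Section 6.0, Aim 1, first Reach index).** A multivariable logistic regression relates baseline characteristics to receipt of counseling or medication. Its covariates are given only as examples, so site is neither named nor excluded.

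**The concern.** Leaving a stratification factor out of a model matters little for a treatment effect that was randomized within strata. It matters more for Aim 2, whose target is the predictors. In Section 6.0, H2 ranks mental distress and active substance abuse above all other baseline predictors, and the plan wants to use the results to direct later interventions. These are observational associations. A characteristic that is merely more common at a site with more quitting can look like a predictor, and one that is common at a site with less quitting can be masked.

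The documents show ways in which site could matter. Medication requests go to each facility's own program or provider, who need not prescribe, and control participants receive a list of local services (Section 5.6). Recruitment takes all women and "a random sample of men to total 5,000 potential participants from each site" (Section 5.3), so the mailed share of women at a site is its number of eligible women divided by 5,000. Sex is one of the eight Aim 2 covariates.

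**Working it through.** **1. The plan's own figure.** The only power statement concerns the primary comparison: 4% against 6.4%, 1,920 per group, two-sided 5%, 90% power (Section 6.0, Power calculations). With the pooled-variance test:
- Mean proportion 0.052. Null SE = √(2 × 0.052 × 0.948 / 1,920) = 0.00717.
- Alternative SE = √((0.04 × 0.96 + 0.064 × 0.936) / 1,920) = 0.00716.
- Power = Φ((0.024 − 1.96 × 0.00717) / 0.00716) = Φ(1.39) = 0.918.

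This agrees with the stated 90%. The point made here does not alter it. No power is stated for Aim 2.

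**2. How far omitting site can move a predictor.** The documents give no abstinence rate or covariate mix by site, so every site value here is an assumption. Take four equal sites (3,840 / 4 = 960), with abstinence q and prevalence x of a characteristic independent within each site. The true within-site OR is then 1.00. Pool the expected counts:
- a = Σ 960·x·q, b = Σ 960·x·(1 − q), c = Σ 960·(1 − x)·q, d = Σ 960·(1 − x)·(1 − q)
- OR = ad / bc and SE(log OR) = √(1/a + 1/b + 1/c + 1/d)

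Worked case: q = 4.0, 4.5, 5.5, 6.5% and x = 15, 30, 40, 60%. Then a = 77.28, b = 1,314.72, c = 119.52, d = 2,328.48. OR = 1.145, SE = 0.150, and log OR / SE = 0.9.

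| Site abstinence (%) | Prevalence (%) | Crude OR, same ranking | Crude OR, reversed | log OR / SE, same ranking |
|---|---|---|---|---|
| 4.0, 4.5, 5.5, 6.5 | 25, 30, 35, 40 | 1.05 | 0.95 | 0.3 |
| 4.0, 4.5, 5.5, 6.5 | 15, 30, 40, 60 | 1.15 | 0.87 | 0.9 |
| 3, 4, 6, 8 | 25, 30, 35, 40 | 1.10 | 0.91 | 0.6 |
| 3, 4, 6, 8 | 15, 30, 40, 60 | 1.30 | 0.76 | 1.8 |

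The table puts the two quantities in perfect or exactly reversed rank order. Over all 24 orderings of the 15–60% prevalences, the median distortion, taken as a ratio away from 1 in either direction, is 1.07 for the narrower abstinence range and 1.15 for the wider. If either x or q is equal across sites, the OR is exactly 1.00.

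The 1.8 is the largest value in this table, not a bound. Prevalences of 10, 25, 45, 60% with abstinence of 3–8% give OR 1.36, about 2.1 SE (0.309 / 0.147).

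**3. Treatment effect.** The planned rates imply OR = (0.064 / 0.936) / (0.04 / 0.96) = 1.64. With 1:1 allocation within each site, reference-arm abstinence of 3, 4, 6, 8% and a within-site OR of 1.64, the OR pooled over sites is 1.63. Omitting site hardly changes it.

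**4. Cost of adding site.** Expected abstinent participants at 12 months: 0.04 × 1,920 + 0.064 × 1,920 = 76.8 + 122.9 = 199.7, about 200. Four sites need three indicator terms.

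**The case against.** The strongest reply is that nothing in the documents shows site confounding. It needs site differences in abstinence and in the characteristic, and neither is reported. Section 5.6 says that pharmacotherapy is available at all sites. The sampling rule makes the share of women vary only if sites differ in their number of eligible women, and no counts are given. Sex is also not an H2 predictor, and no text shows distress or substance abuse varying by site. All of this stands, and it limits the point to a risk.

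The illustration is also crude. It is a single-time 2×2 calculation, whereas the planned model adjusts jointly for eight covariates, and some of these could absorb part of a case-mix difference. This stands too. The figures show a possible size and do not predict one.

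A third reply is that the omission is only a missing detail: the listed covariates are described as patient-level, and the blocked design is declared under Aim 1. This does not succeed for the Aim 2 model. That model is specified by its levels, its treatment term and its covariates, and fitting it as written leaves site out. The reply does have force for the treatment-receipt regression, whose open list does not exclude site.

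**Conclusion.** The omission is on the page and has no stated reason. Its consequence is conditional: if sites differ in both abstinence and a characteristic, the Aim 2 estimate for that characteristic can mix a patient effect with a site difference. Under the assumed ranges in the table, a null association appears as a crude OR of about 1.05 to 1.30, or 0.95 to 0.76 if reversed, at most about 1.8 standard errors. A shift below two standard errors is still not negligible for a ranking. In the two scenarios with prevalence 15–60%, a nominal 5% test of a characteristic with no within-site effect would reject about 15% and 43% of the time.

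A reader might infer more: that the Aim 2 estimates are biased, that every site difference in quitting would be credited to patient characteristics, or that the sampling rule by itself confounds sex with site. The documents support none of these. They contain no site-level data, only the part of a site difference that is correlated with a covariate can be misattributed, and the sex link depends on unreported counts. Nor does the point reach the primary test, which already accounts for site, or the Aim 2 treatment effect, which stratified randomization protects. This is a free improvement to a secondary aim.

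**What to change.** In Section 6.0, Aim 2 Method, state that site enters the model as three fixed indicator terms alongside treatment group and the eight listed covariates, so that predictors are compared within site. Fixed terms are preferable to a random site effect because four sites are too few to estimate a variance well. For consistency, name site as a covariate in the treatment-receipt regression under the first Reach index of Aim 1.

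The cost is a sentence in each place and three parameters against about 200 expected abstinence events in Aim 2. Site is already recorded for every participant, so no new data are needed and no stated sample size or power figure changes. Prespecifying the term also removes a later choice between results with and without site.
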